1. INTRODUCTION

This document details the planned statistical analyses for the Gossamer Bio Inc., protocol "4004002" study titled "A Phase 1A Single Ascending Dose and Multiple Ascending Dose Double-Blind, Placebo-Controlled, Randomized Trial of Oral Inhalation PK10571 in Healthy Adult Subjects".

The proposed analyses are based on the contents of the final version of the protocol (dated 29-June-2018, version 5.0).

This project has two parts

Part A (SAD)

Subjects will receive either PK10571 starting dose of fine particle dose (FPD), PK10571 dose of FPD, or placebo. An optional fifth cohort of up to FPD may be added. Part A will enroll up to 40 subjects; 8 subjects per cohort in a parallel design. The data from each cohort will be analyzed before deciding whether to proceed with the next cohort.

Each cohort will include a sentinel group of 2 subjects (1 active and 1 placebo) who will be dosed at least 48 hours before the remaining subjects (5 active and 1 placebo). Dosing of the remaining subjects will occur following a safety evaluation of the sentinel group.

Subjects will receive one of the treatments listed in Table 1 in randomized fashion.

Table 1 Part A: Planned Doses for Cohorts 1, to 5

Cohort	Test Formula	tion Dose	Placebo	
1 -	PK10571	FPD (n= 6)	Placebo (n=2)	
2 -	PK10571	FPD (n=6)	Placebo (n=2)	
3 -	PK10571	FPD (n=6)	Placebo (n=2)	
4-	PK10571	FPD (n=6)	Placebo (n=2)	
5-	PK10571 up to (n=6)	FPD	Placebo (n=2)	
FPD = fine particle d	ose; n = number of subjects			
Note: Cohort 5 is opt	ional			

Part B (MAD)

Part B is a multiple ascending dose study design. Subjects will receive either PK10571 or placebo. Approximately 24 subjects will be enrolled in Part B. Subjects will be enrolled in up to 3 cohorts of 8 subjects each in a parallel design.

For each cohort, randomization will occur in 2 blocks as follows: In the first block, 2 subjects (sentinel subjects) will be randomized 1:1 to receive PK10571 or placebo; in the second block, 6 subjects will be randomized 5 PK10571: 1 placebo. If PK10571 is well-tolerated in the sentinel subjects, the remainder of the cohort (n = 6) will be randomized. There will be a minimum of 48 hours between dosing of the 2 sentinel subjects and the remainder of the cohort.

The initial dose for Part B will be determined after review of the safety and pharmacokinetic data from Part A.

Data from the lower dose cohort will be analyzed before deciding whether to proceed with the higher dose cohort. Alternately, a lower dose may be administered, depending upon review of the previous cohort's safety and pharmacokinetic data.

Subjects will receive one of the treatments listed below in randomized fashion.

Table 2 Part B: Planned Doses for Cohorts 1, 2 and 3

Cohort	Test Formulation (n = 6)	Placebo (n = 2)	
1	PK10571 initial dose	Placebo	OCHRESCO CONTRACTOR
2	PK10571 middose*	Placebo	
3	PK10571 high dose*	Placebo	

n = number of subjects

Note: Each subject will receive a dosing according to the assigned treatment either once daily (QD), twice daily (BID), or three times daily (TID) for 7 consecutive days. For TID dosing, each daily administration will be separated by 6 hours.

* Alternately, Cohort 2 or 3 will receive a lower dose, depending upon safety and pharmacokinetic data from Cohort 1 or 2, respectively.

2. STUDY OBJECTIVES

The objectives of this study are:

- To determine the safety and tolerability of single ascending inhalation doses of PK10571 formulated as a dry powder with subjects (Part A)
- To determine the safety and tolerability of multiple ascending inhalation doses of PK10571 formulated as a dry powder with subjects (Part B)
- To evaluate the bioavailability of PK10571 following single- and multiple-dose regimens

3. ENDPOINTS

3.1. Primary Endpoint

The safety endpoints are the incidence of treatment-emergent events (TEAEs), physical examination findings, and changes in vital signs, pulmonary function and electrocardiogram (ECG) measurements.

Pharmacokinetic (PK) endpoints are the summary of the pharmacokinetic parameters (e.g. C_{max}, AUC_{last}, and AUC_{inf}) for PK10571 across treatments, dose-linearity assessment and steady state assessment (after multiple dosing)

4. SAMPLE SIZE

Forty subjects will be dosed in Part A of this study.

Twenty-four subjects will be dosed in Part B of this study.

The sample size is not based on statistical considerations. The number of subjects planned for enrollment is considered sufficient to achieve the study objectives.

5. RANDOMIZATION

Subjects will be randomized into one dose cohort and receive either PK10571 or placebo. Within each cohort, 6 subjects will receive active drug and 2 subjects will receive placebo.

For both the SAD and MAD parts each cohort, randomization will occur in 2 blocks as follows: In the first block, 2 subjects (sentinel subjects) will be randomized 1:1 to receive PK10571 or placebo; in the second block, 6 subjects will be randomized 5 PK10571: 1 placebo. If PK10571 is well-tolerated in the sentinel subjects, the remainder of the cohort (n = 6) will be randomized. There will be a minimum of 48 hours between dosing of the 2 sentinel subjects and the remainder of the cohort.

Gender distribution will be based on sequential screening of volunteers who meet entry criteria, with a minimum of 4 females per cohort, in order to ensure 2 females per active dose group. Subjects will be assigned numbers in an ascending order, based on successful completion of the screening process. Each subject will participate in only one cohort.

Subjects who withdraw from the study may be replaced at the discretion of the Principal Investigator and Sponsor.

6. PLANNED ANALYSES

No statistical analysis plan (SAP) prepared in advance of the data can be absolutely definitive and the final clinical study report (CSR) may contain additional tables or statistical tests if warranted by the data obtained. The justification for any such additional analyses will be fully documented in the final CSR.

6.1. Analysis Population

The populations for Part A and Part B will be tabulated both separately and overall.

6.1.1. Safety Population

The Safety Population is defined as all subjects who received any study drug.

6.1.2. PK Population

The PK population is defined as all subjects who received active study drug and have at least one quantifiable postdose concentration.

6.2. Derived Data

This section describes the derivations required for statistical analysis. Unless otherwise stated, variables derived in the source data will not be re-calculated.

6.2.1. Age

Age at date of first dose will be calculated in SAS. To ensure age is correctly derived across all timepoints including leap days the following logic is to be used.

age = floor ((intck('month', birthdate,date) - (day(date) < day(birthdate))) / 12);

Note: Date = Date of first dose of study drug.

This logic will calculate the age in years relative to date of Birth and date of first dose of study drug.

6.2.2. Race

Where more than one race category has been selected for a subject, these race categories will be combined into a single category labeled "Multiple Race" in the summary tables. The listings will reflect the original selected categories.

6.2.3. Baseline

Baseline is defined as the last non-missing value (either scheduled, unscheduled or repeat) before the subject receives the first dose of study drug in both Part A and Part B.

6.2.4. Early Terminations Assessments

End-of-study (EoS) procedures will be performed on Day 11 of Part A and on Day 35 of Part B. Early Termination (ET) will be included with (EoS) tabulations.

6.2.5. Duration/Study Day/Time

Study day will be calculated as the number of days from first dose of study drug for both Part A and Part B.

- date of event date of first dose of study drug + 1, for events on or after first dose
- date of event date of first dose of study drug, for events before first dose.

6.2.6. Conventions for Missing and Partial Dates

It is not expected that there will be any missing dates; however, in the rare case that an adverse event (AE) start date or time is missing and it is unclear whether the AE is treatment emergent or not, then a conservative approach will be taken, and it will be assumed that the AE occurred after first dosing.

All dates presented in the individual subject listings will be as recorded on the eCRF.

6.2.7. Exposure to Study Drug

Exposure to study drug will be calculated as follows from the date of last dosing minus the first day of dosing + 1. The exposure calculation will not take into account breaks in therapy.

6.2.8. Inexact Values

In the case where a safety laboratory variable is recorded as "> x", " \geq x", " \leq x" or " \leq x", a value of x will be taken for analysis purposes.

6.2.9. Unscheduled Visits

Only scheduled values will be tabulated. Post-baseline repeat/unscheduled assessments will be disregarded, although these post-baseline assessments will be listed in the relevant appendices to the CSR.

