# Part A

A total of 84 mL (14 x 6 mL samples) will be collected from each subject in Part A for pharmacokinetic analysis.

In addition, approximately 114 mL of blood will be collected for laboratory evaluations. The total volume of blood collected from each subject will not exceed approximately 198 mL. Additional blood may be collected if necessary for repeat laboratory evaluations or AE follow up.

Blood samples collected up to and including 24 hours postdose within  $\pm 2$  minutes of scheduled time will not be considered deviations. Blood samples collected after 24 hours through 48 hours within  $\pm 5$  minutes of scheduled time will not be considered deviations. Blood samples collected after 48 hours postdose within  $\pm 10$  minutes of scheduled time will not be considered deviations.

Table 4 Total Amount of Blood to be Collected for Testing in Part A

| Reason for Collection   | Number of
Samples | Volume per
Sample (mL) | Total Volume (mL) |
|---|----------------------|---------------------------|-------------------|
| Clinical labs at screening                                      | 1                    | 25                        | 25                |
| Clinical labs during study (check-in, 24 and 48 hours postdose) | 3                    | 15                        | 45                |
| Clinical labs at end-of-study                                   | 1                    | 15                        | 15                |
| Platelet aggregation  | 2                    | 6.5                       | 13                |
| Buffy coat samples  | 2                    | 8                         | 16                |
| Pharmacokinetic analysis  | 14                   | 6                         | 84                |
|   |                      | Total                     | 198               |

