#### CONFIDENTIAL

31 Jul 2018

blood pressure in each arm at screening, then at other times the subject may have blood pressure measured in the dominant arm. Should one set of blood pressure measurements be out of range, the blood pressure reading will be repeated in the same arm.

For purposes of qualifying any given subject for study participation, out-of-range vital signs may be repeated once.

Additional vital signs measurements may be performed as deemed medically necessary by research personnel. All vital signs measurements will be taken after the subject has completed a minimum 3-minute sit.

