5.10.2 Pulmonary Function Tests (Spirometry)

Part A: Pulmonary function tests (FEV1 and FVC; best of 3 reproducible maneuvers) will be performed at screening, check-in, at 1, 8, and 24 hours after dose administration, and at the end of the study (Day 11).

Part B: In the case of QD dosing, pulmonary function tests (FEV1 and FVC; best of 3 reproducible maneuvers) will be performed at screening, check-in, at 1, 4, 8, and 23 hours after administration of the first and last morning doses (Day 1 and Day 7), 1 hour after dosing on Day 4, on Day 14, and at the end of the study (Day 35).

In the case of BID dosing, pulmonary function tests (FEV1 and FVC; best of 3 reproducible maneuvers) will be performed at screening, check-in, at 1, 4, 8, and 23 hours after administration of the first morning dose on Day 1 and Day 7, at least 1 hour after the first dose on Day 4, on Day 14, and at the end of the study (Day 35).

In the case of TID dosing, pulmonary function tests (FEV1 and FVC; best of 3 reproducible maneuvers) will be performed at screening, check-in, and at 1 hour after the first morning dose on Day 1, Day 4, and Day 7, at least 1 hour before second dose on Day 1 and Day 7, 23 hours after the first morning dose on Day 1 and Day 7, on Day 14 and at the end of the study (Day 35).

Repeat spirometry will be allowed at the Investigator's discretion.

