6.12.2. Laboratory Data

For Part A and Part B, the following analysis will be undertaken separately. Descriptive statistics of the observed values and change from baseline (continuous data) will be presented by treatment and visit for each hematology (including coagulation), urinalysis, and serum chemistry (including fasting lipid panel and fasting glucose) parameter. Each measurement (continuous data) will be classed as below, within, or above normal range, based on ranges supplied by the laboratory used. Shift tables in relation to the normal range from baseline to each follow-up visit will be presented.

A listing of any clinically significant laboratory measurements recorded throughout the study will be presented.

All laboratory data, will be listed for example:

- Serology testing: hepatitis B, hepatitis C, and HIV
- Urine drug, alcohol, and cotinine screen tests.
- Serum pregnancy tests (all female subjects)
- FSH tests (female subjects claiming post-menopausal status)

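### The SAP keeps repeat and unscheduled post-baseline safety values out of its summary tables and plans no worst-post-baseline summary, so the most extreme observed value can appear only in a listing

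*SAP*

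**What the plan says.** SAP 6.2.9 sets one rule for all tabulated data: "Only scheduled values will be tabulated. Post-baseline repeat/unscheduled assessments will be disregarded". The same sentence goes on: "although these post-baseline assessments will be listed in the relevant appendices to the CSR". SAP 6.3 adds that all data are listed.

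The planned summaries of measured safety data are in SAP 6.12.2 to 6.12.5. Laboratory data have observed values and changes by visit, and for shifts the text reads: "Shift tables in relation to the normal range from baseline to each follow-up visit will be presented". Vital signs have observed values and changes at each visit. FEV1 and FVC have observed values and changes from baseline. ECG variables have changes at each visit and a shift in overall interpretation to each follow-up visit. The output list in SAP Appendix 1 (14.3.6.1 and 14.3.7.1 to 14.3.7.11) matches this and has no worst-post-baseline table.

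The protocol expects some measurements outside the schedule:

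- Blood (Protocol 5.7, repeated in Appendices 4 and 5): "Additional blood may be collected if necessary for repeat laboratory evaluations or AE follow up".
- Vital signs (Protocol 5.10.1): "Additional vital signs measurements may be performed as deemed medically necessary by research personnel".
- Spirometry (Protocol 5.10.2): "Repeat spirometry will be allowed at the Investigator's discretion".

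Protocol 5.10.4 makes no provision for unscheduled or repeat ECGs.

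**The concern.** Restricting by-visit means to scheduled values is ordinary practice, because it keeps time points comparable. The difficulty is that nothing else in the plan picks the other values up. SAP 6.3 promises a minimum and maximum for each continuous variable, and a reader will take these as the extremes observed. Under 6.2.9 they are the extremes among scheduled values only.

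Safety is the main question of this first-in-human inhaled study, and SAP 3.1 names changes in vital signs, pulmonary function and ECG among the primary safety endpoints. At least some off-schedule measurements will be taken because something needed following up. If such a measurement is the subject's worst, the summary tables for that dose group can look better than the data collected.

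**Working it through.** The plan states no figure for this point, so there is nothing to reproduce. The check sets the sources of off-schedule values against the outputs that could show them.

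| Data | Stated reason for extra measurement | Planned summary | Where an off-schedule value appears |
|---|---|---|---|
| Laboratory | Repeat test or AE follow-up | Change by visit; shift to each visit | Appendix listings; also 14.3.4.1 if clinically significant |
| Vital signs, oximetry | Medical necessity | Change by visit | Appendix listing 16.2.8.9 |
| FEV1, FVC | Investigator's discretion | Change from baseline | Appendix listing 16.2.8.13 |
| ECG | None stated | Change and interpretation shift by visit | Appendix listing 16.2.8.10, if any exist |

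No row has a summary table that would include the off-schedule value. Only laboratory data have a listing placed with the Section 14 tables. The loss arises in two ways: an unscheduled measurement is more extreme than every scheduled one, or a repeat is worse than the scheduled value it repeats.

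**Room between scheduled laboratory visits.** Postdose chemistry and hematology fall on Days 2, 3 and 11 in Part A, and on Days 2, 4, 7, 9, 14 and 35 in Part B (Protocol 5.7 and Section 12). The longest gaps are 11 − 3 = 8 days and 35 − 14 = 21 days. A sample drawn for AE follow-up inside a gap may be the only measurement near the peak. The gaps are a feature of the schedule and are not caused by 6.2.9.

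**Weight of one subject.** SAP Section 5 gives 6 active subjects per cohort. One subject missing from the extremes is 1/6 = 16.7% of the dose group, and two are 2/6 = 33.3%.

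**Illustration, resting on an assumption that is not in the documents.** Let q be the probability that an active subject's worst value is measured only off schedule, independently between subjects. The chance that the tables miss at least one subject's worst value is 1 − (1 − q)^6 per cohort. For the full 5 × 6 = 30 active subjects of Part A it is 1 − (1 − q)^30.

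| q | One cohort (n = 6) | Part A (n = 30) |
|---|---|---|
| 2% | 11.4% | 45.5% |
| 5% | 26.5% | 78.5% |
| 10% | 46.9% | 95.8% |
| 20% | 73.8% | 99.9% |

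The documents do not say which q is realistic. The table shows only that a small rate per subject adds up over a study part.

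**The case against.** The strongest reply is that nothing is lost from the report. The values are listed, and with 8 subjects per cohort a listing can be read in full. Clinically significant laboratory values from the whole study have their own listing (14.3.4.1). Protocol 6.1.1 lets an abnormal finding be an adverse event, and one reported as such enters the TEAE tables whatever 6.2.9 says. Early-termination values are tabulated with end of study (SAP 6.2.4). SAP Section 6 allows further tables if the data call for them. All of this stands. It limits the point to summary tables of measured values; it does not supply the missing summary, and for spirometry, vital signs and ECG there is no counterpart to 14.3.4.1.

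The rule can also work in the cautious direction. Protocol 5.10.1 has an out-of-range blood pressure repeated in the same arm. Under 6.2.9 the out-of-range scheduled reading stays in the table and a normal repeat cannot replace it. A reader might infer that the dropped values are selectively the abnormal ones, or that adverse events trigger all the extra tests. The documents do not support that: AE follow-up is a stated reason only for blood, alongside repeat testing, and for spirometry only discretion is stated.

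A reader might also call the rules asymmetric, since baseline is the "last non-missing value (either scheduled, unscheduled or repeat) before the subject receives the first dose". That is not a defect in itself. Baseline needs one reference value, whereas postdose summaries need comparable time points, and no bias follows from the difference.

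**Conclusion.** The point holds in a limited form. Followed as written, the SAP's summary minima, maxima and shifts for laboratory data, vital signs and spirometry can omit the most extreme value observed. The same applies to ECG if unscheduled tracings are taken. One such subject is 16.7% of an active dose group. How often it would happen cannot be derived from the documents.

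Two stronger readings should be resisted. First, a reader might estimate the loss from the Part A spirometry times of 1, 8 and 24 hours. Assuming uniform onset over 24 hours, a 2-hour fall overlaps a scheduled test for (1 + 2 + 2)/24 = 20.8% of onsets, and a 4-hour fall for (1 + 4 + 4)/24 = 37.5%. The remainder measures schedule coverage, not the effect of 6.2.9: a fall that nobody measures is absent under any tabulation rule. Second, a reader might infer that dose escalation rests on incomplete tables. Protocol 3.3 has the Safety Review Committee assess all available safety data, so the effect is on the study report summaries and not on conduct.

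This is a worthwhile, inexpensive improvement. No stated analysis fails without it.

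**What to change.** Leave the by-visit tables on scheduled values. Add a sentence to SAP 6.2.9, with matching entries in 6.12.2 to 6.12.5 and Appendix 1, providing one worst-post-baseline change or shift summary per subject from all scheduled, unscheduled and repeat values. It should cover laboratory parameters (in the direction of concern for each), vital signs and oximetry, FEV1 and FVC, and ECG intervals if any unscheduled tracings exist. Show the number of post-baseline assessments beside it.

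The cost is a few table rows from data already collected, with no extra visits, samples or subjects. The drawback is that subjects measured more often have more chances of an extreme value. The summary must therefore be read with the assessment counts and kept apart from the by-visit statistics.

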### **3.5 Stopping Rules for Dose Escalation**

The following will result in a decision not to continue dose escalation if judged by the Safety Review Committee to be related to study drug:

- 1. Onset of respiratory symptoms postdose suspected to be related to study medication including but not limited to bronchospasm (wheezing), stridor, clinically significant moderate dyspnea, oxygen desaturation with dyspnea, evidence of significant airflow obstruction on spirometry in at least 2 subjects.
- 2. Three-fold increase in aspartate transaminase (AST) or alanine transaminase (ALT) above the upper limit of normal in at least 2 subjects;
- 3. Two-fold increase in creatinine in at least 2 subjects;
- 4. Gastrointestinal (GI) bleed in at least 1 subject;

- 5. New onset atrial fibrillation in at least 1 subject in which case the Safety Review Committee will determine if dose escalation can be undertaken with additional monitoring (such as telemetry)
- 6. Clinically significant decrease in hemoglobin in at least 2 subjects;
- 7. Platelet count drop to less than 60,000 in at least 2 subjects;
- 8. Fifty percent drop in total white blood cell (WBC) count in at least 2 subjects; or
- 9. Two-fold increase in International Normalized Ratio (INR) in at least 2 subjects.

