| Adverse event assessment n            |           |              | •            |         |            |           |           |         |         |         |         | - X      |          |          |          |          |          |         |   |   |   |    |    | → |

BUN = blood urea nitrogen; CR = creatinine; ECG = electrocardiogram; FSH = follicle-stimulating hormone; hr = hours; HIV = human immunodeficiency virus; INR = international normalized ratio; min = minutes; PK = pharmacokinetic; PPD = positive purified protein derivative skin test; PT = prothrombin time; PTT = partial thromboplastin time;  $T_{max}$  = time of maximum concentration; TSH = thyroid stimulating hormone

- a) A full set of vital signs (blood pressure, pulse rate, respiration rate, temperature, and pulse oximetry) will be measured at screening, at 0 hour (predose), and at the end-of-the study visit on Day 35. Blood pressure, pulse rate, and pulse oximetry will be measured 10 minutes after the first dose and at the following hours after the first dose: 1, 4, 8, 12, 16, 24, then daily on Days 3-9 (48, 72, 96, 120, 144, 168, 192, and 216 hours postdose) and at the outpatient visits on Day 10 and 14. At the screening visit, each subject will have blood pressure measured in both arms. If there is no significant difference (i.e., greater than 15 mmHg) between the systolic blood pressure in each arm at screening, then at other times the subject may have blood pressure measured in one arm.
- b) Physical examinations will be conducted for all subjects at screening, predose on Day 1, and on Days 2, 4, 7, 9, 14, and 35.

Gossamer Bio, Inc.

CONFIDENTIAL

31 Jul 2018

- c) All subjects will have ECGs performed at screening and at the following times (relative to the first dose): predose, 20 minutes postdose, 2, 4, 8, and 24 hours postdose, Day 9 (prior to check-out), Day 14, and at the end of the study.
- d) Pulmonary function tests (FEV1 and FVC; best of 3 reproducible maneuvers) to be performed using spirometry. Repeat spirometry will be allowed at the Investigator's discretion.
- e) To be performed at 1, 8, and 24 hours post Day 7 dose.
- f) PPD test to be read 48-72 hours after placement.
- g) Safety labs (chemistry, hematology, coagulation, and urinalysis) will be collected at the following time points: screening, check-in, Day 2, Day 4, Day 7, Day 9, Day 14, and Day 35 (end of study)

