6.12.4. Pulmonary Function Test

For Part A and Part B, the following will be presented separately. Descriptive statistics for observed values and changes from baseline to post dose assessments in the following pulmonary function tests (FEV1 and FVC; best of 3 reproducible maneuvers) will be tabulated by treatment. All pulmonary function test data will be listed.

The details of exploratory analysis are shown in Section 6.11. All statistical output will be listed and figures produced for the scatter plots.

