14.3.7.3b	Serum Chemistry Data, Change from Baseline (MAD) – Safety Population	IP	
14.3.7.4a	Serum Chemistry Data, Normal Range Shifts (SAD) – Safety Population	IP	
14.3.7.4b	Serum Chemistry Data, Normal Range Shifts (MAD)– Safety Population	IP	
14.3.7.5a	Urinalysis Data, Change from Baseline (SAD)— Safety Population	IP	
14.3.7.5b	Urinalysis Data, Change from Baseline (MAD)– Safety Population	IP	
14.3.7.6a	Urinalysis Data, Normal Range Shifts (SAD)– Safety Population	IP	
14.3.7.6b	Urinalysis Data, Normal Range Shifts (MAD) – Safety Population	IP	
14.3.7.7a	Platelet Aggregation Data, Change from Baseline (SAD) – Safety Population	IP	
14.3.7.7b	Platelet Aggregation Data, Change from Baseline (MAD) – Safety Population	IP	
14.3.7.8a	Platelet Aggregation Data, Normal Range Shifts (SAD) – Safety Population	IP	
14.3.7.8b	Platelet Aggregation Data, Normal Range Shifts (MAD) – Safety Population	IP	
14.3.7.9a	ECG Data, Change from Baseline (SAD) – Safety Population		
14.3.7.9b	ECG Data, Change from Baseline (MAD) – Safety Population	IP	

Table Number	Table Title	Validation Method	Shell Number (if repeat)
14.3.7.10a	ECG Data, Overall Interpretation (SAD) – Safety Population	IP	
14.3.7.10b	ECG Data, Overall Interpretation (MAD)– Safety Population	IP	
14.3.7.11a	Pulmonary Function, Change from Baseline (SAD) -Safety Population	IP	
14.3.7.11b	Pulmonary Function, Change from Baseline (MAD) -Safety Population	IP	
14.3.8	Concomitant Medication		
	Not Applicable		
14.4	PK Tables		
14.4.1	Descriptive Statistics for Concentration-Time Data of PK10571 in Plasma after Single Dose Administrations of FPD (Cohort 1), FPD (Cohort 2), FPD (Cohort 3), FPD (Cohort 4), and FPD (Cohort 5) Part A		
14.4.2	Descriptive Statistics for Concentration-Time Data of PK10571 in Plasma after Single Dose Administrations of FPD (Cohort 1), FPD (Cohort 2), FPD (Cohort 3), FPD (Cohort 4), and FPD (Cohort 5) Part A - Stratified by Sex		
14.4.3	Descriptive Statistics for Concentration-Time Data of PK10571 in Plasma after Administration of xx mg FPD (Cohort 1), xx mg FPD (Cohort 2), and xx mg FPD (Cohort 3) on Day 1 Part B		
14.4.4	Descriptive Statistics for Concentration-Time Data of PK10571 in Plasma after Administration of xx mg FPD (Cohort 1), xx mg FPD (Cohort 2), and xx mg FPD (Cohort 3) on Day 1 Part B – Stratified by Sex		

Table Number	Table Title	Validation Method	Shell Number (if repeat)

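### SAP 6.2.9 keeps repeat and unscheduled spirometry out of the lung-function tables, so a transient FEV1 or FVC fall measured only off schedule is listed but not summarised

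*SAP*

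**What the plan says.** SAP 6.2.9 sets one rule for every kind of post-baseline assessment: "Only scheduled values will be tabulated. Post-baseline repeat/unscheduled assessments will be disregarded, although these post-baseline assessments will be listed". SAP 6.12.4 does not exempt spirometry. It states that "pulmonary function tests (FEV1 and FVC; best of 3 reproducible maneuvers) will be tabulated by treatment", as descriptive statistics of observed values and changes from baseline, and that all data will be listed. Appendix 1 contains two spirometry safety tables: 14.3.7.11a for Part A and 14.3.7.11b for Part B, whose title begins "Pulmonary Function, Change from Baseline (MAD". Off-schedule values appear in Listing 16.2.8.13 only.

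Four other provisions matter:
- SAP 3.1 names change in pulmonary function among the safety endpoints.
- SAP 6.2.3 allows the baseline to be an unscheduled or repeat value.
- SAP 6.2.4 tabulates early-termination assessments with end of study.
- Protocol 5.10.2 foresees tests beyond the schedule: "Repeat spirometry will be allowed at the Investigator's discretion".

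**The concern.** This is a first-in-human study of an inhaled powder, and the first stopping rule in Protocol 3.5 is respiratory. It includes "evidence of significant airflow obstruction on spirometry in at least 2 subjects". A subject's lowest measured FEV1 is therefore a number that a reader of the study report will want.

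Under SAP 6.2.9 as written, two things can happen:
1. A fall is measured off schedule, has recovered by the next scheduled test, and is lower than all of that subject's scheduled values. The tables then show a milder picture than the data. A fall that persists to the next scheduled test is tabulated.
2. A scheduled session does not give reproducible maneuvers, its value is recorded all the same, and a valid repeat follows. The tables keep the poor value and ignore the good one. The error then goes the other way.

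The rule is also uneven: a repeat or unscheduled value may serve as baseline but may not appear after it.

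**Working it through.** The documents state no figure for this point, so there is none to reproduce. The check asks how much room the schedule leaves for case 1, and what the fix would cost in chance bias.

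**Inputs (Protocol 5.10.2; dosing from Protocol 3.2 and Appendices 4 and 5).** Hours run from the first dose on Day 1.
- QD: doses at 0, 24, ..., 144; tests at 1, 4, 8, 23, 73, 145, 148, 152, 167.
- BID: doses at 0, 12, ..., 156; tests as for QD. The Day 4 test is set only as "at least 1 hour after the first dose on Day 4" and is taken here at 1 h (73).
- TID: doses at 0, 6, 12 on each day; tests at 1, 5, 23, 73, 145, 149, 167. The 5 h and 23 h tests come from "at least 1 hour before second dose on Day 1 and Day 7, 23 hours after the first morning dose".
- All regimens: further tests on Days 14 and 35.

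**Gap = time of next scheduled test minus time of dose.**
- QD: 1, 49, 25, 1, 49, 25, 1.
- BID: 1, 11, 49, 37, 25, 13, 1, 61, 49, 37, 25, 13, 1, 11.
- TID: 1, 17, 11, 49, 43, 37, 25, 19, 13, 1, 67, 61, 49, 43, 37, 25, 19, 13, 1, 17, 11.

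| | QD | BID | TID |
|---|---|---|---|
| Median gap (h) | 25 | 19 | 19 |
| Longest gap (h) | 49 | 61 | 67 |
| Doses with gap of 8 h or less | 3 of 7 | 3 of 14 | 3 of 21 |
| Doses with gap of 24 h or more | 4 of 7 | 7 of 14 | 10 of 21 |
| Doses with no test before the next dose | 4 of 7 | 9 of 14 | 16 of 21 |

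**Sensitivity.** Table 7 (QD) differs from Section 5.10.2. It marks no Day 4 test, and its footnote for Day 7 reads "To be performed at 1, 8, and 24 hours post Day 7 dose". Under Table 7 the QD median is 49 h if the 24 h test on Day 2 precedes the second dose, and 25 h if it follows that dose by 1 h. With the BID Day 4 test at 4 h, the BID median is 20.5 h. Part A is less exposed: tests fall at 1, 8 and 24 h after the only dose, then on Day 11.

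**Which falls would go untabulated (all values assumed).** Take a 20% fall from 2.4 L (0.20 × 2.4 = 0.48 L) at the second BID dose of Day 1 or 7. The next scheduled test is 11 h later. With exponential recovery of half-life h, that test shows a fall of 20 × 2^(−11/h) percent: 0.4% for h = 2 hours, 5.6% for 6, 10.6% for 12, 14.6% for 24. A fast-recovering fall vanishes from the tables; a slow one largely stays.

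**Chance bias of a minimum over more tests.** Scheduled post-dose tests per subject: Part A 4; QD and BID 4 + 1 + 4 + 2 = 11; TID 3 + 1 + 3 + 2 = 9. For k independent standard normal values the expected minimum is:
- k = 4: −1.029; k = 5: −1.163; difference 0.134.
- k = 9: −1.485; k = 10: −1.539; difference 0.054.
- k = 11: −1.586; k = 12: −1.629; difference 0.043.

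**Noise at fall cut-offs (SD assumed; none is given).** With SD 5% of baseline, the chance that one test shows a fall of at least 10% is Φ(−2) = 0.02275. Over 11 tests, 1 − (1 − 0.02275)^11 = 22.4%; over 12 tests, 24.1%. Among 6 active subjects, at least one such fall appears with probability 1 − 0.776^6, about 78%. For a 15% cut-off, Φ(−3) = 0.00135 gives 1.5% and 1.6% per subject. With SD 3%, the 10% cut-off gives about 0.5% per subject for either number of tests.

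**The case against.** The strongest reply is that the gaps describe the protocol's visit schedule and not the effect of SAP 6.2.9. A fall that nobody measures is missing under any tabulation rule. The rule matters only if an off-schedule test is done, and the protocol speaks of repeat spirometry, not of tests triggered by symptoms. An acute effect that recurs with dosing would be sampled at 1 h after the first dose on Days 1 and 7, and on Day 4 for QD (by Section 5.10.2) and TID. This stands: the gaps show opportunity, not frequency.

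Three further replies also stand, in part:
- A reader might infer that such a fall can never enter the tables. SAP 6.2.4 does not support that. Early-termination values are tabulated with end of study, and Protocol 5.9 includes spirometry among those procedures when possible.
- Case 2 is conditional. The tabulated quantity is the best of three reproducible maneuvers, so a failed session may yield no value at all. The documents do not say how such a session is recorded.
- Laboratory and ECG data have shift tables and spirometry does not, but vital signs, including pulse oximetry, are handled as spirometry is. Spirometry has not been singled out.

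The last reply is that listings, adverse event tables and optional extra tables in the study report (SAP 6) already cover the matter. They do so only partly. An adverse event row gives a term and not the size of the fall. A listing does not set dose groups against pooled placebo. A summary chosen after a fall has been seen is weaker than one fixed beforehand.

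**Conclusion.** The point holds as a reporting gap. Followed as written, SAP 6.2.9 can leave a subject's lowest measured FEV1 or FVC out of the tabulated summary of a named safety endpoint, except when it is taken at an early-termination visit. It also bars a valid repeat from replacing a scheduled value recorded from a non-reproducible session. How often either would occur cannot be worked out from the documents. The Part B medians of 19 to 25 h show only that a short-lived fall could come and go between scheduled tests.

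A reader might go further and infer that respiratory signals would be hidden from dose escalation. The documents do not support this: Protocol 3.3 has the Safety Review Committee assess all available safety data, spirometry included, and every value stays in Listing 16.2.8.13.

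The bias figures assume independent normal noise, and the recovery and cut-off figures rest on assumed values. This is a cheap improvement of low priority.

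**What to change.** 1. **SAP 6.2.9.** For spirometry, a repeat that meets the best-of-three-reproducible-maneuvers standard replaces a scheduled test that does not.
2. **SAP 6.12.4, Tables 14.3.7.11a/b.** Add each subject's lowest post-dose FEV1 and FVC from all valid scheduled, repeat and unscheduled tests, as change in litres and as percent of baseline, by dose and pooled placebo. Beside it, show the same summary from scheduled tests only and the number of tests per subject. By-time-point rows stay scheduled-only.
3. **Optional.** Counts of subjects at fall cut-offs, descriptive only. If they are used, the sponsor should fix the cut-offs in advance and avoid 10% unless within-subject variability is shown to be small.

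The cost is a sentence in 6.2.9 and one block in two planned tables. The values are already collected and listed, and no procedure or protocol change is needed. Item 1 does require that the recorded data show whether a session met the standard, which the sponsor should confirm. The one statistical downside is that a minimum over more tests is slightly lower by chance, which is why the scheduled-only figure and the test counts are shown alongside.
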